#### **8.4.1.1. Reporting SAEs to Pfizer Safety**

All SAEs occurring in a participant during the active collection period as described in [Section 8.4.1](#) are reported to Pfizer Safety using PSSA immediately upon awareness and under no circumstance should this exceed 24 hours, as indicated in [Appendix 3](#). The investigator will submit any updated SAE data to the sponsor within 24 hours of its being available.

#### **8.4.1.2. Recording Nonserious AEs and SAEs on the CRF**

All nonserious AEs and SAEs occurring in a participant during the active collection period, which begins after obtaining informed consent as described in [Section 8.4.1](#), will be recorded on the AE section of the CRF.

The investigator is to record on the CRF all directly observed and all spontaneously reported AEs and SAEs reported by the participant.

As part of ongoing safety reviews conducted by the sponsor, any nonserious AE that is determined by the sponsor to be serious will be reported by the sponsor as an SAE. To assist in the determination of case seriousness, further information may be requested from the investigator to provide clarity and understanding of the event in the context of the clinical study.

Reporting of AEs and SAEs for participants who fail screening are subject to the CRF requirements as described in [Section 5.4](#).

#### **8.4.2. Method of Detecting AEs and SAEs**

The method of recording, evaluating, and assessing causality of AEs and SAEs and the procedures for completing and transmitting SAE reports are provided in [Appendix 3](#).

Care will be taken not to introduce bias when detecting AEs and/or SAEs. Open-ended and nonleading verbal questioning of the participant is the preferred method to inquire about AE occurrences.

#### **8.4.3. Follow-Up of AEs and SAEs**

After the initial AE or SAE report, the investigator is required to proactively follow each participant at subsequent visits/contacts. For each event, the investigator must pursue and obtain adequate information until resolution, stabilization, the event is otherwise explained, or the participant is lost to follow-up (as defined in [Section 7.3](#)).

In general, follow-up information will include a description of the event in sufficient detail to allow for a complete medical assessment of the case and independent determination of possible causality. Any information relevant to the event, such as concomitant medications

and illnesses, must be provided. In the case of a participant death, a summary of available autopsy findings must be submitted as soon as possible to Pfizer Safety.

Further information on follow-up procedures is provided in [Appendix 3](#).

#### **8.4.4. Regulatory Reporting Requirements for SAEs**

Prompt notification by the investigator to the sponsor of an SAE is essential so that legal obligations and ethical responsibilities toward the safety of participants and the safety of a study intervention under clinical investigation are met.

The sponsor has a legal responsibility to notify both the local regulatory authority and other regulatory agencies about the safety of a study intervention under clinical investigation. The sponsor will comply with country-specific regulatory requirements relating to safety reporting to the regulatory authority, IRBs/ECs, and investigators.

Investigator safety reports must be prepared for SUSARs according to local regulatory requirements and sponsor policy and forwarded to investigators as necessary.

An investigator who receives SUSARs or other specific safety information (eg, summary or listing of SAEs) from the sponsor will review and then file it along with the SRSD(s) for the study and will notify the IRB/EC, if appropriate according to local requirements.

#### **8.4.5. Environmental Exposure, Exposure During Pregnancy or Breastfeeding, and Occupational Exposure**

Environmental exposure occurs when a person not enrolled in the study as a participant receives unplanned direct contact with or exposure to the study intervention. Such exposure may or may not lead to the occurrence of an AE or SAE. Persons at risk for environmental exposure include healthcare providers, family members, and others who may be exposed. An environmental exposure may include EDP, EDB, and occupational exposure.

Any such exposures to the study intervention under study are reportable to Pfizer Safety within 24 hours of investigator awareness.

##### **8.4.5.1. Exposure During Pregnancy**

An EDP occurs if:

- A female participant is found to be newly pregnant while receiving or after discontinuing study intervention.
- A male participant who is receiving or has discontinued study intervention inseminates a female partner.
- A female nonparticipant is found to be pregnant while being exposed or having been exposed to study intervention because of environmental exposure. Below are examples of environmental EDP:

- A female family member or healthcare provider reports that she is pregnant after having been exposed to the study intervention by ingestion.
- A male family member or healthcare provider who has been exposed to the study intervention by ingestion then inseminates his female partner prior to or around the time of conception.

The investigator must report EDP to Pfizer Safety within 24 hours of the investigator's awareness, irrespective of whether an SAE has occurred. The initial information submitted should include the anticipated date of delivery (see below for information related to termination of pregnancy).

- If EDP occurs in a participant or participant's partner, the investigator must report this information to Pfizer Safety using the EDP Supplemental form within PSSA, regardless of whether an SAE has occurred. Details of the pregnancy will be collected after the start of study intervention and until a minimum of 28 calendar days after the last administration of study intervention.
- If EDP occurs in the setting of environmental exposure, the investigator must report information to Pfizer Safety using PSSA. Since the exposure information does not pertain to the participant enrolled in the study, the information is not recorded on a CRF; however, a copy of the completed case report from PSSA is maintained in the investigator site file.

Follow-up is conducted to obtain general information on the pregnancy and its outcome for all EDP reports with an unknown outcome. The investigator will follow the pregnancy until completion (or until pregnancy termination) and notify Pfizer Safety of the outcome as a follow-up using PSSA. In the case of a live birth, the structural integrity of the neonate can be assessed at the time of birth. In the event of a termination, the reason(s) for termination should be specified and, if clinically possible, the structural integrity of the terminated fetus should be assessed by gross visual inspection (unless preprocedure test findings are conclusive for a congenital anomaly and the findings are reported).

Abnormal pregnancy outcomes are considered SAEs. If the outcome of the pregnancy meets the criteria for an SAE (ie, ectopic pregnancy, spontaneous abortion, intrauterine fetal demise, neonatal death, or congenital anomaly in a live-born baby, a terminated fetus, an intrauterine fetal demise, or a neonatal death), the investigator should follow the procedures for reporting SAEs. Additional information about pregnancy outcomes that are reported to Pfizer Safety as SAEs follows:

- Spontaneous abortion including miscarriage and missed abortion should be reported as an SAE;
- Neonatal deaths that occur within 1 month of birth should be reported, without regard to causality, as SAEs. In addition, infant deaths after 1 month should be reported as

SAEs when the investigator assesses the infant death as related or possibly related to exposure to the study intervention.

Additional information regarding the EDP may be requested by the sponsor. Further follow-up of birth outcomes will be handled on a case-by-case basis (eg, follow-up on preterm infants to identify developmental delays). In the case of paternal exposure, the investigator will provide the participant with the Pregnant Partner Release of Information Form to deliver to his partner. The investigator must document in the source documents that the participant was given the Pregnant Partner Release of Information Form to provide to his partner.

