### 2.3.1. Risk Assessment

Potential Risk of Clinical Significance	Summary of Data/Rationale for Risk	Mitigation Strategy
Study Intervention(s): Nirmatrelvir		
Emesis	In Study C4671005, vomiting occurred at a greater frequency in the nirmatrelvir/ritonavir group than in the placebo group.	AEs will be monitored, and participants may receive antiemetics if needed.
Hypertension	Transient increases in systolic, diastolic, and mean blood pressure were observed in the preclinical studies. In Study C4671005 (adults at high risk for severe disease), a small imbalance in hypertension AEs (1% vs <1%) was reported.	Vital signs and all AEs will be monitored in the study. Refer to Section 8.4 .
Reduced maternal and fetal weight	In rabbit embryo-fetal development toxicity studies, nirmatrelvir-related lower maternal body weight change and food consumption were observed at 1000 mg/kg/day but were not considered adverse based on low magnitude of difference from control and lack of impact on absolute body weights. Nirmatrelvir -related, adverse, lower fetal weight (0.91x control) was observed at 1000 mg/kg/day.	Lower dose of 300 mg q12h is used in this study.
Study Intervention(s): Ritonavir		
Gastrointestinal disturbances (including diarrhea, nausea, vomiting and abdominal pain)	Frequently reported adverse reaction in HIV-positive patients who are HIV-positive at 600 mg BID.	Lower dose of 100 mg twice daily is used in this study. There will be close observation of AEs. In addition to ongoing review of AEs by the sponsor, an E-DMC will review safety data as described in Section 10.1.5.1 .  Taking study intervention with food may improve tolerability.
Neurological disturbances (eg, paresthesia, including oral paresthesia, dysgeusia and dizziness)	Frequently reported adverse reaction in patients who are HIV-positive at 600 mg BID.	Lower dose used in this study. There will be close observation of AEs.

Potential Risk of Clinical Significance	Summary of Data/Rationale for Risk	Mitigation Strategy
		In addition to ongoing review of AEs by the sponsor, an E-DMC will review safety data as described in Section 10.1.5.1 .

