### **Other Exclusion Criteria:**

12. Females who are pregnant up to <14 weeks gestation. Pregnancy  $\geq$ 14 weeks is not exclusionary.
13. Investigator site staff directly involved in the conduct of the study and their family members, site staff otherwise supervised by the investigator, and sponsor and sponsor delegate employees directly involved in the conduct of the study and their family members.

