#### **8.4.1. Time Period and Frequency for Collecting AE and SAE Information**

The time period for actively eliciting and collecting AEs and SAEs (“active collection period”) for each participant begins from the time the participant provides informed consent, which is obtained before undergoing any study-related procedure and/or receiving study intervention, through and including a minimum of 28 calendar days, except as indicated below, after the last administration of the study intervention.

Follow-up by the investigator continues throughout the active collection period and until the AE or SAE or its sequelae resolve or stabilize at a level acceptable to the investigator.

When a clinically important AE remains ongoing at the end of the active collection period, follow-up by the investigator continues until the AE or SAE or its sequelae resolve or stabilize at a level acceptable to the investigator and Pfizer concurs with that assessment.

For participants who are screen failures, the active collection period ends when screen failure status is determined.

If the participant withdraws from the study and also withdraws consent for the collection of future information, the active collection period ends when consent is withdrawn.

If a participant permanently discontinues or temporarily discontinues study intervention because of an AE or SAE, the AE or SAE must be recorded on the CRF and the SAE reported using the PSSA.

After the defined active collection period for safety events, long-term follow-up visits are also conducted at Weeks 12 and 24. Any new SAE occurring during this long-term follow-up period and determined to be related to study intervention must be reported to Pfizer Safety immediately upon awareness and under no circumstance should this exceed 24 hours.

Investigators are not obligated to actively seek information on AEs or SAEs after the participant has concluded study participation. However, if the investigator learns of any SAE,

including a death, at any time after a participant has completed the study, and they consider the event to be reasonably related to the study intervention, the investigator must promptly report the SAE to Pfizer using the PSSA.

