### **10.4.2. Female Participant Reproductive Inclusion Criteria**

The criteria below are part of Inclusion Criterion 1 (Age and Sex; [Section 5.1](#)) and specify the reproductive requirements for including female participants. Refer to [Section 10.4.4](#) for a complete list of contraceptive methods permitted in the study.

- A female participant is eligible to participate if at least 1 of the following conditions applies:
  - Is not a WOCBP (see definition in Section 10.4.3).
    - OR
  - Is a WOCBP who is pregnant (at least 14 weeks gestation).
    - OR
  - Is a WOCBP who is not pregnant at screening and agrees to use a highly effective contraceptive method (failure rate of  $< 1\%$  per year) during the intervention period and for at least 28 days after the last dose of study intervention, which corresponds to the time needed to eliminate any reproductive safety risk of the study intervention(s). If a highly effective, user-dependent method is chosen, she agrees to concurrently use an effective barrier method of contraception. The investigator should evaluate the effectiveness of the contraceptive method in relationship to the first dose of study intervention.

The investigator is responsible for review of medical history, menstrual history, and recent sexual activity to decrease the risk for inclusion of a woman with an early undetected pregnancy.

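### The protocol does not require follow-up to pregnancy and neonatal outcome for women who are already pregnant at the first dose, although it does for other exposed pregnancies

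*Protocol*

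**What the plan says.** **Eligibility.** Protocol Section 5.2, criterion 12, excludes "Females who are pregnant up to <14 weeks gestation" and states that later pregnancy is not exclusionary. Section 10.4.2 makes pregnancy of at least 14 weeks one of the conditions under which a female participant qualifies.

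**Definition.** Section 8.4.5.1 gives three routes to an EDP:

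- a participant: "A female participant is found to be newly pregnant while receiving or after discontinuing study intervention";
- the female partner of a male participant;
- a nonparticipant: "A female nonparticipant is found to be pregnant while being exposed or having been exposed to study intervention because of environmental exposure".

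**Consequence of an EDP.** The same section requires a report within 24 hours with the anticipated delivery date, and a supplemental form for participants and partners. It then says: "Follow-up is conducted to obtain general information on the pregnancy and its outcome for all EDP reports with an unknown outcome". It adds: "The investigator will follow the pregnancy until completion (or until pregnancy termination) and notify Pfizer Safety of the outcome". The reporting table in Section 10.3.3 (Appendix 3) has a broader row heading, but its operative text uses the term EDP. It has no row for pregnancy at entry.

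**General safety collection.** Section 8.4.1 collects AEs and SAEs from consent to at least 28 days after the last dose. After that: "Any new SAE occurring during this long-term follow-up period and determined to be related to study intervention must be reported".

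**Why pregnancy is on the protocol's agenda.** The risk table (Section 2.3.1) lists reduced maternal and fetal weight, noting from rabbit studies that "adverse, lower fetal weight (0.91x control) was observed at 1000 mg/kg/day". Section 4.2.2 calls human reproductive safety data limited. The synopsis, under Ethical Considerations, names preterm birth, low birth weight and stillbirth among the outcomes that treatment might improve for pregnant participants.

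**The concern.** A woman enrolled while pregnant has certain, dated exposure to 5, 10 or 15 days of active drug. Hers is the most informative pregnancy the trial can observe, yet the word *newly* leaves her outside the definition that starts outcome follow-up. A family member who accidentally swallows a tablet while pregnant falls inside it.

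Followed as written, the protocol could leave the trial without birth outcomes for the pregnancies it chose to expose. Normal outcomes would be missing too, so any abnormal outcome that did surface would have no denominator. Information not sought at the time may not be recoverable later.

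**Working it through.** The plan states no figure on this point. The check is a reading of the text, followed by date arithmetic.

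**1. Does a woman pregnant at entry meet any part of the EDP definition?**

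- *Participant.* She must be found newly pregnant during or after study intervention. A woman whose pregnancy of at least 14 weeks was established at screening is not newly pregnant. The qualifier appears deliberate: the nonparticipant part omits it, and the breastfeeding definition in Section 8.4.5.2 has no equivalent. Section 7.1 also speaks separately of participants who become pregnant during the study.
- *Partner of a male participant.* Not applicable.
- *Nonparticipant.* Not applicable.

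She meets none of the three.

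**2. Does anything else require her outcome?** The pregnancy-test row of the Schedule of Activities concerns women not pregnant at screening. AE monitoring is scheduled to Day 44 or early termination. The legible items at Weeks 12 and 24 include vital status, symptoms and COVID-19-related visits, but no pregnancy or delivery item. The safety outputs in SAP Section 6.5 name no pregnancy outcome.

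**3. How far does general collection reach into a pregnancy?**

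Inputs: last dose on Day 15 or 16 (Schedule of Activities); at least 28 further days (Section 8.4.1); Week 24 at Day 168 (SAP Appendix 2.1). Delivery at 40 weeks, range 37 to 42, is my assumption and is not in the documents.

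- End of active collection: 15 + 28 = Day 43, or 16 + 28 = Day 44. Day 44 is 43 days after Day 1, and 43/7 = 6.1 weeks.
- Gestation at Day 44 for entry at 14 weeks: 14 + 6.1 = 20.1 weeks.
- Gestation at Week 24 for entry at 14 weeks: 14 + 167/7 = 37.9 weeks.
- Earliest entry that delivers by Day 44 = delivery week − 6.1:

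| Assumed delivery (weeks) | Entry needed (weeks) |
|---|---|
| 37 | 30.9 |
| 40 | 33.9 |
| 42 | 35.9 |

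- For entry at 14 weeks, delivery comes 23 to 28 weeks later (37 − 14 to 42 − 14). That is 161 to 196 days after Day 1, or Day 162 to Day 197, against a Week 24 target of Day 168.

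So for women entering before about 34 weeks (range 31 to 36), delivery falls after active collection ends.

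**The case against.** The strongest reply is that the trial is far from blind to these pregnancies, and much of that reply stands.

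- All AEs and SAEs are collected to about Day 44, so a fetal loss or stillbirth in that window is captured whether or not an EDP report exists.
- Section 8.4.5.1 treats abnormal pregnancy outcomes as SAEs and makes neonatal death within 1 month reportable regardless of causality. These sentences sit in the EDP section, so their reach to women pregnant at entry is arguable, but they are a partial safety net.
- Under Section 10.3.3, an event whose cause the investigator does not know is handled as related. A late loss or anomaly of uncertain cause is therefore reportable once the site learns of it. Section 8.4.1 also requires reporting of reasonably related SAEs learned of after study completion.

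A reader might therefore infer too much in three ways. It would be wrong to say that no pregnancy outcome would be collected, for the reasons above. It would be wrong to say that outcome data could come only from accidental conceptions, because EDP also covers nonparticipants who were already pregnant when exposed. And it would be wrong to say that only women pregnant at entry lack birth-weight data: birth weight and gestational age at delivery are not named for EDP pregnancies either. The stated mitigation for the fetal-weight risk is the dose used; the protocol never promises to monitor fetal weight.

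What the reply does not supply is anyone asking. A duty to report an SAE once known is not a duty to find out the outcome. Preterm birth and low birth weight are not in the listed SAE outcomes, and a normal delivery after Day 44 reaches no form that the protocol describes.

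**Conclusion.** The gap is real and narrow. As written, the protocol does not require systematic follow-up to pregnancy and neonatal outcome for participants pregnant at the first dose, while it does for newly pregnant participants, partners of male participants and environmentally exposed nonparticipants.

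Its size depends on gestation at entry. With delivery assumed at 40 weeks (range 37 to 42), only entry at about 34 weeks or later (range 31 to 36) places delivery inside active collection. It is tempting to turn this into a proportion of women: (33.9 − 14)/(40 − 14) = 76%. That is a share of eligible gestational weeks. It would be a share of women only if entry were spread evenly over them, and the documents give no basis for that. The number of pregnant entrants is not stated; it may be small or zero.

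The conclusion is about what the protocol text requires. Sites may follow these pregnancies anyway, and the consent pages, CRF and EDP supplemental form were not available to check. No endpoint, estimand or planned analysis is affected. The case for changing the text is that exposure is certain in these women, human data are described as limited, and the remedy is cheap.

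**What to change.** In Section 8.4.5.1, add a part to the EDP definition for a female participant who is pregnant at the time of the first dose of study intervention. The existing 24-hour report, supplemental form and follow-up to completion then apply to her without a new process. Align the exposure row of the Section 10.3.3 table, and reconcile both with Sections 5.2 and 10.4.2.

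Recording gestational age at delivery and birth weight for all EDP pregnancies is a reasonable low-cost addition, given the fetal-weight finding in the risk table. A summary of these pregnancies by arm in the study report is a preference only.

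Cost: a few sentences in an amendment, one report per pregnant entrant, and outcome follow-up that for some women runs past the Week 24 visit. No treatment or eligibility rule changes.

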#### **8.4.5.2. Exposure During Breastfeeding**

An EDB occurs if:

- A female participant is found to be breastfeeding while receiving or after discontinuing study intervention.
- A female nonparticipant is found to be breastfeeding while being exposed or having been exposed to study intervention (ie, environmental exposure). An example of environmental EDB is a female family member or healthcare provider who reports that she is breastfeeding after having been exposed to the study intervention by ingestion.

The investigator must report EDB to Pfizer Safety within 24 hours of the investigator's awareness, irrespective of whether an SAE has occurred. The information must be reported using the PSSA. When EDB occurs in the setting of environmental exposure, the exposure information does not pertain to the participant enrolled in the study, so the information is not recorded on a CRF. However, a copy of the completed SAE Case Report from PSSA is maintained in the investigator site file.

An EDB report is not created when a Pfizer drug specifically approved for use in breastfeeding women (eg, vitamins) is administered in accordance with authorized use. However, if the infant experiences an SAE associated with such a drug, the SAE is reported together with the EDB.

